modulators such as fingolimod and siponimod in multiple sclerosis, monitoring for these specific safety parameters is planned for this study [43,44]. This monitoring includes PFTs, cardiac monitoring at first dose and on treatment re-initiation after a defined period of treatment interruption, liver function tests, and ophthalmoscopy with optical coherence tomography (OCT). Based on its mechanism of action, etrasimod is expected to dose-dependently reduce lymphocyte counts. This reduction is reversible, with lymphocyte counts returning to within normal limits following study drug discontinuation. Lymphocyte reduction may increase the risk of infections in some subjects. Thus, serial assessment of white blood cell (WBC) count and differential will be performed to assess the risk for serious and atypical infections and study subjects will be closely monitored by Investigators. Subjects with low lymphocyte count in circulation, or who have active infections will be excluded in this study.

S1P receptor modulators are associated with an expected, on-target, dose-dependent effect of reducing heart rate (HR) upon first dosing with HR recovery to predose baseline thereafter [45]. There have been no reported cases of symptomatic bradycardia on first dose, and rare first- or second-degree atrioventricular (AV) block found on ECG has been asymptomatic and transient (ie, spontaneous resolution) with etrasimod. An S1P₁-mediated HR reduction is maximal on the first day of dosing with etrasimod and typically peaks approximately 3 hours postdose on Day 1 with recovery thereafter. In Study APD334-003, the mean transient HR decrease did not exceed 10 beats per minute (bpm) on Day 1 up to 8 hours after dosing in all treatment groups, with the mean nadir of HR lowering for 2 mg etrasimod occurring 3 hours after dosing [38]. Therefore, a dose-escalation regimen is not necessary for doses up to 2 mg.

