9.4. Extension Treatment Period

9.4.1. Week 24 Visit

The Week 24 visit will be used to assess eligibility for the Extension Treatment Period and is considered the beginning of the Extension Treatment Period. During this visit, eligibility for

entry into the Extension Treatment Period will be confirmed (ie, meets eligibility criteria; Section 4.3).

At the Week 24 visit, vital signs should be measured first, followed by ECG, predose PK sample collection, study drug dosing at the study site, and first-dose cardiac monitoring (direct observation) for at least 4 hours in all subjects continuing in the Extension Treatment Period. Cardiac monitoring is required because there is a subset of subjects who will transition from placebo in the Double-Blind Treatment Period to an etrasimod dose in the Extension Treatment Period. Refer to Section 10.6.7.4 for detailed guidance on first-dose cardiac monitoring and subject discharge criteria postdose.

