10.6.7.4. Guidance for Cardiac Monitoring Following Treatment Initiation or Re-Initiation

Cardiac monitoring following treatment initiation applies to the first dose administered in the Double-Blind Treatment Period (Day 1) and in the Extension Treatment Period (Week 24). The lowest predose HR measurement (by vital signs) will be used for comparison to the postdose measurement (by vital signs). Subjects should receive the first dose of study treatment before 12:00 PM (noon).

First-Dose Heart Rate Monitoring

Cardiac monitoring of at least 4 hours following the first dose (Day 1 and Week 24) will include the following ([Table 4](#)):

- Full baseline vital signs (HR, BP, body temperature, and respiratory rate) and 12-lead ECG will be assessed predose (ie, Baseline)
- After the first dose of study treatment (Day 1 and Week 24), subjects must remain under direct observation at the study site for at least 4 hours.
- At Hours 1, 2, and 3 (\pm 15 minutes) postdose, the HR and BP will be assessed with the subject in the seated position, with the time recorded. If the subject has an HR < 50 bpm evaluate cardiac rhythm by 12-lead ECG to identify any clinically relevant ECG changes.
- At the Hour 4 (\pm 15 minutes) discharge assessment, HR and BP will be assessed with the subject in the seated position and a 12-lead ECG in the supine position will also be performed. Subjects may be discharged from the study site after the Hour 4 assessment if they meet the discharge criteria described in [Table 5](#). Subjects not meeting the discharge criteria will require extended monitoring as described below.
- Subjects experiencing a treatment-related symptomatic event (eg, chest pain, dizziness, palpitations, lightheadedness, shortness of breath, or syncope) associated with reduction of the HR together with clinically relevant 12-lead ECG changes at any time during the 4-hour monitoring period should be discontinued from study treatment.

Table 4: Procedures to Be Performed During the Cardiac Monitoring Period

Procedure	Predose	Hours 1, 2, and 3 Postdose^a	Hour 4 Postdose^a
Blood pressure and heart rate ^b	X	X	X
12-lead ECG	X		X
Assess discharge criteria			X

^a Measurements may be taken \pm 15 minutes of the scheduled time.

^b Heart rate is based on vital signs.

ECG, electrocardiogram

Table 5: Discharge Criteria After Cardiac Monitoring

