Subjects will be released from the study site after dosing on Day 1 or Week 24 (but no sooner than 4 hours postdose) when they fulfill all of the following discharge criteria:

• Heart rate \geq 50 bpm or no more than 10 bpm lower than the predose value

• Heart rate is not the lowest value measured during the observation period

• No evidence of second-degree AV block or higher

• No cardiac symptoms (eg, chest pain, dizziness, palpitations, lightheadedness, shortness of breath, or syncope)^a

^a Subjects experiencing a symptomatic event (eg, chest pain, dizziness, palpitations, lightheadedness, shortness of breath, and/or syncope) at any time during the 4-hour monitoring period that is not associated with either a reduction in HR or clinically relevant change in 12-lead ECG, may be discharged provided they meet the other discharge criteria, and deemed appropriate by the Investigator.

Note: Subjects should have written instructions on when to return to the study site and a 24-hour contact phone number to call in the event of any new or worsened cardiovascular symptoms.

AV, atrioventricular; bpm, beats per minute; ECG, electrocardiogram; HR, heart rate

Extended Cardiac Monitoring

Subjects who do not meet discharge criteria at 4 hours postdose will require extended cardiac monitoring:

- Vital signs (BP and HR) will be assessed hourly and a 12-lead ECG may be performed, as clinically indicated, until the subject meets the discharge criteria (Table 5)
- The Medical Monitor should be contacted if the subject does not meet the discharge criteria after \geq 4 hours of extended cardiac monitoring

If an ECG shows a new onset QTcF interval above 500 ms (CTCAE Grade 3), a repeat ECG is warranted, and, if this abnormal finding is confirmed and is considered related to study treatment, then study treatment must be interrupted. Effective diagnostic and therapeutic strategies should be employed.

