^b Subjects discontinuing prior to Week 24 should have an ET visit within 7 days of the last study treatment administration and before initiation of any new treatments. Note that safety evaluations (eg, AE query, review of concomitant medications, symptom-directed and focused physical exams as needed and relevant laboratory assessments) will be performed as described in Section 10.6.

^c Medical history will be collected during Screening and should be updated for any new conditions or medications as needed prior to dosing at the Week 0/Day 1 visit (Section 10.3.4).

^d eDiary device and training should be provided at Screening to ensure capturing of entries within the required 14-day period.

^e Study site staff will monitor subject eDiary compliance. During Screening, the completion of the following eDiary questionnaires should be monitored: DSQ (daily), FAQ (daily), PGIS (Day -8 and Day -1). At least 8 DSQ daily entries in the last 2 weeks prior to Week 0/Day 1 (Baseline) visit as well as completion of PGIS are needed for

- randomization. During the Treatment Period, the completion of the following eDiary questionnaires should be monitored: DSQ (daily), FAQ (daily), PGIS (Weeks 15, 16, 23, and 24), PGIC (Weeks 16 and 24), EoE-QOL-A (Week 0/Day 1 and Weeks 16 and 24).
- ^f Safety vital signs (resting HR and systolic and diastolic BP, body temperature, and respiratory rate) taken with subjects in the sitting position will be performed at Screening and prior to randomization on Week 0/Day 1 (Baseline). Vital signs may be repeated up to 2 times during a visit to confirm abnormal readings (no need for second reading if the first reading is normal). Inclusion and exclusion criteria related to vital signs and ECG must be reviewed and reassessed to confirm eligibility. Vital signs including HR and BP must be measured first, followed by 12-lead ECG. The 12-lead ECGs should be obtained prior to predose blood sample collection. The first-dose cardiac monitoring procedure (Section 10.6.7.4) should be repeated if a subject has a dose interruption of: 1) ≥ 2 consecutive days within the first week of treatment during the Double-Blind Treatment Period or during Week 24; or 2) ≥ 7 consecutive days after the first week of treatment during the Double-Blind Treatment Period or after Week 24.

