 - ^m Screening EGD (Section 10.3.6) and biopsies (Section 10.3.6.1) should be performed preferably within the first 7 days of the screening period visit to allow sufficient time to confirm histology eligibility. The eosinophil counts from the central reader must be available for confirmation of eligibility. The EREFS will be scored by personnel performing the EGD. If the ET visit is within 4 weeks of the last EGD and biopsy, these procedures do not need to be repeated.
 - ⁿ PK blood samples are to be collected predose (for trough level, within 60-minute period prior to dosing) and 4 hours (± 15 minutes) postdose on Week 0/Day 1 (after 12-lead ECG), and predose on all other indicated days. A PK sample should be taken, if possible, at the time of any SAE or AE leading to study treatment discontinuation. For all PK blood draws, the time of the last dose should be documented.

CCI

- ^p Study drug may be dispensed by secure mail per country specific guidance. Alternatively, a future supply of study medications may be dispensed to the subject at a site visit to cover study medications to be dispensed at the Telehealth Visit.
- ^q Study treatment should be dispensed at Week 24 if the subject continues treatment in the Extension Treatment Period. Additionally, subjects who continue on study but do not enter the Extension Treatment Period on the same day as the Week 24 visit may also be dispensed bridging study treatment.
- ^r At each site visit, previously dispensed medication bottles and any remaining tablets will be collected and counted by the Investigator or qualified staff. The number of remaining tablets in the bottle may be counted by visual inspection via videoconferencing for virtual assessment. The bottle(s) and any remaining tablets must be returned to the site at the next site visit.
- ^s On study visit days with blood draws, subjects should take their dose of study treatment after predose assessments and procedures have been completed.
- ^t The visit window is 14 days following Week 24 visit.

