If one or more results for a variable are assigned to the same analysis visit, the result with the date closest to the protocol scheduled day will be used in the analysis. If two measurements in the same analysis visit window are equidistant from the protocol scheduled study day, the earlier measurement will be used in the analysis. If multiple assessments are available on the same day, then the average of the assessment will be used in the analysis, except for laboratory and ECG data where the assessment at the earliest time of the same day will be used. If both central and local assessments of the same lab test are available on the same day, the central result will take precedence over the local result. If both central and local assessments of the same ECG test are available on the same day, the assessment of clinical significance by local reader will take precedence over the determination by a central reader.

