APPENDIX 1. PROGRAMMING CONVENTIONS FOR OUTPUTS

Output Conventions

Outputs will be presented as shown in the Output shells.

Decimals, Percentages, and P-Values

- If the original data has N decimal places, then the summary statistics should have the following decimal places:
 - Minimum and maximum: N
 - Mean (and LS Means), median (and Q1, Q3): N + 1
 - SD or SE: N + 2
 - Percentages will be reported to one decimal place. Where counts are zero, percentages will not appear in the output.
 - P-values will be reported to four decimal places, except values <1.000 but >0.999 will be presented as '>0.999' (e.g., 0.9998 is presented as >0.999); and
 - values <0.0001 will be presented as '<0.0001' (e.g., 0.00009 is presented as <0.0001). Rounding will be applied after the <0.0001 and >0.999 rule.

Dates & Times

Depending on data available, dates and times will take the form DDMMYYYY or DDMMYYYY:hh:mm.

Spelling Format

English US.

Presentation of Treatment Groups

For outputs, treatment groups will be represented as follows and in that order:

Treatment Group	For Tables and/or Graphs	For Listings
etrasimod 2 mg	etrasimod 2 mg	etrasimod 2 mg
etrasimod 1mg	etrasimod 1 mg	etrasimod 1 mg
etrasimod any dose*	etrasimod any dose	Placebo
Placebo	Placebo	Screen Failure
Screen Failure	Screen Failure	

Treatment Group	For Tables and/or Graphs	For Listings
Not Treated**	Not Treated	Placebo

* To be used for tables and/or graphs only.

** To be used for subjects in safety listings who are randomized but do not receive study drug.

Presentation of Visits

For outputs, visits will be represented as follows and in that order when applicable:

Visit Name*	Study Period
Screening	Screening
Baseline, Day 1, Week 2, Week 4, Week 8, Week 16, Week 20, Week 24	Double-Blind Treatment
Week 28, Week 32, Week 46, Week 52	Extension Treatment
2-Week Follow-Up, 4-Week Follow-Up	Safety Follow-Up

- *If a visit is not available for a certain analysis, it won't be displayed

LISTINGS

All listings will be ordered by the following (unless otherwise indicated in the template):

- Randomized treatment group (or treatment received if it's a safety output), first by Etrasimod 2 mg, Etrasimod 1 mg, then Placebo, then Screen Failure and then No Treatment (only in safety listings if there are any randomized subjects who did not receive study drug)
- Subject number (which is expected to incorporate study site/center),
- Date (where applicable)

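### SAP 18.5.1 puts its 500 ms limit on QT where the protocol uses QTcF, and SAP 6.4 averages readings taken after the first etrasimod dose into the Week 24 heart rate and blood pressure of placebo subjects who start the extension that day

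*SAP*

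**What the plan says.** **ECG.** Protocol 11.9.5 plans an outlier analysis of subjects with QTcF above 500 ms or a rise of more than 60 ms from baseline. Protocol 10.6.7.4 also expresses its 500 ms threshold in QTcF. SAP 18.5.1 lists, as absolute criteria, QTcF of at least 450 ms (men) or 470 ms (women) and QT above 500 ms. It adds rises of more than 30 and 60 ms in QT and QTcF. QTcF above 500 ms is not a category. SAP 3.3 enters "not applicable" under changes from the protocol.

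**Vital signs.** SAP 6.4 places vital signs under its visit windows (Week 24 is Days 156 to 183). When one day has several assessments, "then the average of the assessment will be used in the analysis, except for laboratory and ECG data"; those two data types take the earliest reading of the day. SAP Appendix 1 assigns "Baseline, Day 1, Week 2, Week 4, Week 8, Week 16, Week 20, Week 24" to the double-blind period.

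At Week 24, protocol 9.4.1 calls for a predose measurement, dosing on site and at least 4 hours of monitoring for everyone continuing, because "there is a subset of subjects who will transition from placebo in the Double-Blind Treatment Period to an etrasimod dose". Under protocol 10.6.7.4, at Hours 1, 2 and 3 "the HR and BP will be assessed with the subject in the seated position, with the time recorded", and both are measured again at Hour 4. Protocol 1.2 states that the "HR reduction is maximal on the first day of dosing with etrasimod and typically peaks approximately 3 hours postdose" on Day 1, and also that heart rate recovers to its predose level after first dosing.

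**The concern.** The QT mismatch means that an outlier count promised in the protocol is replaced by a different one that depends on heart rate, and the SAP does not record the replacement.

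The averaging rule mixes treatments. A Week 24 value shown under placebo in the double-blind summary would, for same-day starters, consist mostly of readings on etrasimod. SAP 6.3 also admits all post-baseline measurements to summaries of abnormalities. Low heart rates recorded after the first etrasimod dose may therefore be counted as Week 24 placebo abnormalities. At stake is whether the Week 24 heart rate, blood pressure and QT tables describe the groups that they are labelled with.

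**Working it through.** The plan states no figure of its own on either point, so there is none to reproduce.

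**1. QT against QTcF.** Fridericia's formula is QTcF = QT / (60/HR)^(1/3), so QT = QTcF × (60/HR)^(1/3). The two are equal only at HR = 60 bpm.

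| Case | Calculation | Result | Consequence |
|---|---|---|---|
| QTcF 501 ms at 70 bpm | 501 × (60/70)^(1/3) | QT 475.9 ms | meets the protocol limit, missed by the SAP's 500 ms row |
| QTcF 501 ms at 80 bpm | 501 × (60/80)^(1/3) | QT 455.2 ms | missed |
| QT 501 ms at 50 bpm | 501 / (60/50)^(1/3) | QTcF 471.5 ms | counted by the SAP row, below the protocol limit |

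For a QTcF of 520 ms, QT exceeds 500 ms only below 60 / (500/520)^3 = 67.5 bpm.

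**2. Weight of post-dose readings in the Week 24 value.** Weight = post-dose readings / all readings that day.

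- As scheduled (one predose, Hours 1 to 4): 4/5 = 0.80.
- With two predose repeats (protocol Table 7, note f: "Vital signs may be repeated up to 2 times during a visit to confirm abnormal readings"): 4/7 = 0.57.
- With four more hours of extended monitoring (protocol 10.6.7.4: "Vital signs (BP and HR) will be assessed hourly and a 12-lead ECG may be performed"): 8/9 = 0.89. The weight is therefore largest in subjects who failed the discharge criteria.

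**3. Size in same-day starters.** Let F be the mean fall from predose over Hours 1 to 4. On the scheduled readings the Week 24 heart rate is lowered by (4 × F)/5 = 0.8F, that is 0.8 bpm for each 1 bpm of fall. The documents do not give F. Protocol 1.2 reports only that, in the ulcerative colitis Phase 2 study, the mean Day 1 decrease did not exceed 10 bpm. Carrying that ceiling over gives at most 0.8 × 10 = 8.0 bpm, which is a bound and not an estimate.

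**4. Size in the placebo column.** Let s be the share of placebo subjects with Week 24 data who start the extension that day. The column mean is lowered by b = 0.8 × s × F. The documents do not give s. For an assumed s of 50% to 100%, b is 0.4 to 0.8 bpm per 1 bpm of fall.

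**5. Direction of the group difference.** Let d be the true etrasimod minus placebo heart-rate difference at Week 24, and assume that a continuing dose has no same-day effect. The table then shows d + b. If d is negative and larger in size than b, the difference looks smaller than it is. If heart rate has recovered and d is zero, the table shows a spurious difference of b, with etrasimod appearing higher. The documents do not give d.

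**The case against.** On vital signs, the averaging rule can be read as meant for repeats of one assessment and not for separately scheduled timepoints. SAP 18.6 tabulates Week 24 by timepoint against predose, and that table is unaffected. Protocol 9.4.1 treats Week 24 as the start of the extension, and SAP 18 analyses safety by period. SAP 6.2 defines the extension baseline by date and time before the first extension dose. All of this shows that a split at that dose is probably intended. It does not supply one: no SAP rule takes the monitoring readings out of the Week 24 by-visit value, and Appendix 1 labels that visit double-blind. A programmer who follows SAP 6.4 literally would average all five.

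On ECG, the practical loss is limited. Every QTcF above 500 ms also meets the 450/470 ms criterion, the rise of more than 60 ms is kept, and SAP 18.5 lists the ECGs of affected subjects over time. That stands. What is missing is the tabulated count that the protocol specifies.

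It also stands that these tables are descriptive and that SAP 18 plans no between-group safety tests unless otherwise specified.

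**Conclusion.** Both points hold on the text as written, and both are confined to descriptive safety outputs. The QTcF discrepancy is a direct, undeclared conflict between SAP 18.5.1 and protocol 11.9.5. The averaging point follows from applying SAP 6.4 literally. It affects heart rate and blood pressure in placebo subjects who start the extension on the Week 24 visit day. Protocol Table 7, note q, foresees "subjects who continue on study but do not enter the Extension Treatment Period on the same day as the Week 24 visit"; those subjects are not affected. For same-day starters the effect on heart rate is 0.8 times the mean Hour 1 to 4 fall.

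Stronger readings are not supported:

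- A reader might infer that the lowered placebo heart rate hides an etrasimod effect. Protocol 1.2 reports recovery after first dosing, so the difference could shrink or be created. For blood pressure the documents give no direction at all.
- A reader might infer a bias of several bpm. The fall and the share of same-day starters are unknown, and only the reading weights come from the documents.
- A reader might infer that this table drives dose selection. Protocol 6.5 refers to a Week 24 dose selection analysis but names no table, and SAP 4.1 leaves the choice of outputs to a separate list.
- A reader might infer that a heart-rate-lowering drug makes the QT rule misleading throughout. The reported lowering is a first-dose effect with recovery, and by-visit ECG values use the earliest reading of the day. The slow-heart-rate case therefore bears mainly on ECGs taken 4 hours after a first dose.

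**What to change.** 1. In SAP 18.5.1, add QTcF above 500 ms as an absolute criterion and carry it into the ECG incidence and shift tables. The QT row can stay beside it.
2. In SAP 6.4, state that the Week 24 by-visit heart rate and blood pressure use only readings before the first extension dose, averaging any predose repeats, with date and time applied as in SAP 6.2. Keep later readings in the by-timepoint and extension outputs, and out of the double-blind by-visit and abnormality summaries.

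The cost is SAP wording and programming. No assessment is added and no reading is lost, since protocol 10.6.7.4 already has the times recorded. The one small downside is that a Week 24 value resting on one predose reading, or the mean of its repeats, is slightly noisier than a five-reading mean.

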10.6.8.1.4. Adverse Events of Special Interest

Based on the mechanism of action of etrasimod and prior experience with other agents acting via a similar mechanism, potential adverse events of special interest (AESIs) will be identified. In addition to appropriate reporting of these events as an AE or SAE, supplementary detailed information may be collected.

Potential AESI for etrasimod include but are not limited to:

- Cardiovascular events (eg, bradycardia, AV conduction delay, and hypertension)
- Macular edema
- Pulmonary events (airflow obstruction or altered gas exchange)
- Infections (severe infections, opportunistic infections, Herpes simplex, and Herpes zoster)
- Liver injury
- PRES
- Malignancies

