6.2. BASELINE

Unless otherwise specified, Baseline for the Double-Blind Treatment Period is defined as the last non-missing measurement taken prior to the first dose (including unscheduled assessments), and Baseline for the Extension Treatment Period is defined as the last non-missing measurement taken prior to the date of first dose in Extension Treatment Period at Week 24. If measurements include time (except for Quality of Life assessments (QoL)), the date/time will be used to define Baseline. Otherwise, only dates will be compared. QoL baseline is measured on Day 1 prior to the first dose. In the case where the last non-missing measurement and the date of first dose coincide and time is not collected, if the measurement was planned in the protocol to be done prior to the date of first dose, that measurement will be considered in defining Baseline.

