18.5. ECG EVALUATIONS

ECGs are recorded on a 12-lead ECG machine and read locally and centrally. The following ECG parameters will be reported for this study:

HR (bpm)

PR Interval (ms)

RR Interval (ms)

QRS Interval (ms)

QT Interval (ms)

QTcF Interval (ms)

Overall interpretation of ECG (Investigator's judgment):

- Normal
- Abnormal, Not Clinically Significant (Abnormal NCS)

- Abnormal, Clinically Significant (Abnormal CS)

Overall interpretation of ECG (central reader):

- Normal
- Abnormal, Not Clinically Significant (Abnormal NCS)
- Abnormal, Clinically Significant (Abnormal CS)

The following summaries will be provided for ECG data:

- Value and change from Baseline by visit (for quantitative measurements)
- Incidence of markedly abnormal values (defined in Section 17.4.1) by visit
- Shift in normal/abnormal NCS/abnormal CS in the overall interpretation (by investigator) from Baseline to end of treatment and to the worst-case post-Baseline
- Shift in markedly abnormal categories from Baseline to post-Baseline by visit

All ECG results, including first dose cardiac monitoring, will be listed. Discharge criteria for first dose cardiac monitoring will also be listed.

A listing of all ECG assessments over time in subjects meeting markedly abnormal criteria will also be provided. For each subject, only ECG parameters ever meeting markedly abnormal criteria will be included.

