18.6. VITAL SIGNS

The following Vital Signs measurements will be reported for this study:

- Systolic Blood Pressure (mmHg)
- Diastolic Blood Pressure (mmHg)
- Heart Rate (bpm)
- Respiratory Rate (resp/min)
- Temperature (°C)
- Weight (kg)
- Height (cm) [Screening only]

The following summaries will be provided for vital signs data:

- Value and change from Baseline by visit
- Value and change from predose on Day 1 and Week 24 (as reported on the eCRF) by timepoint
 - For heart rate only, also include value and change from predose to minimum postdose heart rate on Day 1 in the same table
- Incidence of markedly abnormal values (defined in section 17.5.2) by visit
- Listing of subjects meeting markedly abnormal criteria
- Incidence of minimum heart rate on Day 1 by postdose timepoint (1, 2, 3, 4, and > 4 hours postdose, and Day 1 overall) and heart rate interval (≥ 65 , 60 to 64, 55 to 59, 50 to 54, 45 to 49, 40 to 44, < 40 bpm)
 - If minimum heart rate is attained at multiple postdose timepoints, only the earliest timepoint will be counted in this incidence summary
- Time to minimum heart rate on Day 1 by planned hourly timepoint (if minimum heart rate is attained at multiple postdose timepoints, only the earliest timepoint will be counted). Actual time elapsed from first dose to minimum heart rate on Day 1 will also be summarized using descriptive statistics (n, mean, SD, median, minimum, and maximum) in the same table.

All vital signs, including first dose cardiac monitoring, will be listed. Discharge criteria first dose cardiac monitoring will also be listed. A listing of all vital signs assessments over time in subjects meeting markedly abnormal criteria will also be provided. For each subject, only vital sign parameters ever meeting markedly abnormal criteria will be included.

For subjects with extended monitoring, systolic blood pressure, diastolic blood pressure and heart rate values and change from predose on Day 1 will be listed.

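### No planned table is sure to show post-dose PR change by arm: by-visit summaries keep the earliest ECG of the day, and ECGs have no by-timepoint table

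*SAP*

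**What the plan says.** **Collection.** Protocol 10.6.7.4 (text and Table 4) requires an ECG before the first dose of each treatment period, Day 1 and Week 24. At the Hour 4 assessment, "a 12-lead ECG in the supine position will also be performed". In the double-blind schedule (Protocol Table 7) the only ECG visits are Screening, Day 1, Week 24 and early termination.

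**Selection.** SAP 6.4 assigns ECGs to analysis visits: Day 1 is study day 1, Week 24 is days 71 to 267, and Week 52 is anything later. Within a visit the date closest to the scheduled day is used. Several results on that day are averaged, "except for laboratory and ECG data where the assessment at the earliest time of the same day will be used".

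**Baseline.** Under SAP 6.2 Baseline is the last non-missing value before the first dose. Where a time is recorded, "the date/time will be used to define Baseline". SAP 6.4 labels that record Baseline and also has a separate Week 0 (Day 1) row. SAP Appendix 1 likewise displays Baseline and Day 1 as two visits.

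**Tables.** For ECGs, SAP 18.5 lists "Value and change from Baseline by visit (for quantitative measurements" and no table by time after dose. PR is one of the reported parameters. For vital signs, SAP 18.6 adds "Value and change from predose on Day 1 and Week 24 (as reported on the eCRF) by timepoint". The markedly abnormal ECG criteria in SAP 18.5.1 cover QT and QTcF only.

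**Risk named in advance.** The AESI list in Protocol 10.6.8.1.4 includes "Cardiovascular events (eg, bradycardia, AV conduction delay, and hypertension".

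**The concern.** The 4-hour tracing is the scheduled post-dose ECG in first-dose monitoring. Protocol 1.2 says the heart-rate effect is greatest on the first day of dosing, and that the rare AV block seen with etrasimod was found on ECG, without symptoms, and passed. Adverse event reporting prompted by symptoms could miss such an effect; a summary of PR intervals would not depend on symptoms.

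Apart from early termination, no ECG is scheduled between Day 1 and Week 24. The Day 1 4-hour tracing is therefore the only scheduled placebo-controlled ECG comparison after a first dose. The Week 24 tracing plays the same part, without a concurrent placebo arm, for subjects who move from placebo to etrasimod.

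Protocol 11.9.5 says intervals including PR will be summarised and that post-baseline ECGs will be compared with baseline. SAP 3.3 declares no change from the protocol. If the by-visit table keeps only predose tracings, that comparison is made without the tracing taken to detect the effect.

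**Working it through.** The plan gives no figure to reproduce here. The check applies the SAP's rules to the scheduled tracings and counts how many are affected.

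**1. Counts.** Inputs: about 96 subjects, randomised 3:3:2 to 1 mg, 2 mg and placebo (Protocol synopsis).
- Each etrasimod arm: 96 × 3/8 = 36. Placebo: 96 × 2/8 = 24.
- First etrasimod doses on Day 1: 36 + 36 = 72, with 24 concurrent placebo doses.
- First etrasimod doses at Week 24: at most 24. This assumes no dropout and that every placebo subject enters the extension.

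**2. Which tracing each row receives.** The PR values below, in ms, are assumed for illustration and are not trial data. Baseline is the last predose value. The row value is the earliest tracing on the selected day, and change is row value minus Baseline.

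| Assumed tracings | Baseline | Day 1 change if the Baseline record may fill the row | Day 1 change if the Baseline record is kept out | Week 24 change |
|---|---|---|---|---|
| A. Day 1: 160 predose, 185 at 4 h. Week 24: 162 predose, 187 at 4 h | 160 | 160 − 160 = 0 | 185 − 160 = +25 | 162 − 160 = +2 |
| B. Day 1: 202, then 192 predose; 215 at 4 h. Week 24: 195 predose, 214 at 4 h | 192 | 202 − 192 = +10 | 202 − 192 = +10 | 195 − 192 = +3 |
| C. Screening 158; no Day 1 predose tracing; 185 at 4 h. Week 24: 162 predose, 187 at 4 h | 158 | 185 − 158 = +27 | 185 − 158 = +27 | 162 − 158 = +4 |

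Case A is the ordinary one. Case B can arise because Protocol 4.2 allows a second assessment after an exclusionary first result.

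**3. What a by-timepoint table would show.** In case A the change from predose to 4 hours is 185 − 160 = +25 on Day 1 and 187 − 162 = +25 at Week 24. The by-visit table shows 0 or +25 on Day 1, depending on the reading, and +2 at Week 24. In case B the Day 1 change is 215 − 192 = +23, against +10 in the by-visit table.

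**4. Reading the results.**
- Week 24: the predose tracing is kept and the 4-hour tracing dropped in all three cases. This follows whenever a predose tracing was taken that day.
- Day 1: the row may hold a value of no change, a post-dose change, or the difference between two predose tracings. Under the literal rule, a subject with a single predose tracing contributes 0.
- PR has no category in SAP 18.5.1, so the abnormality tables do not pick up a numeric PR change either.

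**The case against.** The strongest reply is that the SAP does use the 4-hour ECGs, and much of this stands.

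- SAP 6.3 counts all measurements in summaries of abnormalities and worst-case values, so these tracings enter the QT and QTcF incidence tables.
- SAP 18.5 includes a shift of the investigator's overall interpretation to the worst post-Baseline result. It also lists every first-dose ECG and the discharge criteria.
- SAP 18.2.6 has ECG data reviewed for AESIs that investigators may not have identified, with AV conduction delay as a subcategory tabulated by treatment group.
- The Week 24 predose ECG is the right end-of-double-blind value for the by-visit table. Subjects continuing 1 mg or 2 mg are not taking a first dose then.
- Protocol 11.9.5 asks for outlier analysis of QTcF only, so the lack of a PR category is consistent with the protocol.
- Safety is descriptive (SAP 18), so no planned test is affected. The table shells are in a separate file and might contain more.

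A reader might infer that the Day 1 ECG change is zero for every subject, or that first-dose PR effects are hidden. The documents support neither. Zero requires that the Baseline record also fill the Day 1 row, which the SAP leaves open, and that there be a single predose tracing. Nor can an effect be called hidden when the tracings are listed in full and reviewed for AESIs.

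A reader might also infer that heart rate at the switch to etrasimod goes untabulated. It does not: the vital signs table by timepoint covers Week 24. Only displays such as "Time to minimum heart rate on Day 1 by planned hourly timepoint" are confined to Day 1.

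None of these provisions promises the numeric change in PR after dosing, by arm. The worst-case shift is categorical, not specific to PR and not tied to the first dose. The AESI review depends on cases being recognised one at a time.

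**Conclusion.** The point holds as a gap in the specified tables. At Week 24 the 4-hour ECG enters no value or change table, provided a predose ECG was taken that day. On Day 1 it is left out on the literal reading. On the other reading it would normally fill the Day 1 row, and two programmers could properly produce different tables. No specified table is sure to show post-dose PR change by arm, although AV conduction delay is a named AESI.

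At the planned sample size this concerns the Day 1 4-hour tracings of 96 subjects (72 on etrasimod, 24 on placebo) and, for first etrasimod doses at Week 24, at most 24 subjects. What is at risk is a descriptive safety comparison. Efficacy, the QT and QTcF abnormality counts and heart rate by timepoint are unaffected.

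**What to change.** 1. Add to SAP 18.5: value and change from predose at 4 hours on Day 1 and Week 24 for HR, PR, QRS and QTcF, by treatment group, with placebo-to-etrasimod subjects shown separately at Week 24. This mirrors the vital signs table.
2. State in SAP 6.4 that the Baseline record does not also fill the Week 0 (Day 1) row. Case B shows that this sentence alone is not enough, because a repeat predose tracing could still be chosen. The table in item 1 is the main remedy.

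Optional:
- A descriptive count of PR at or above 200 ms by arm. This is the limit that Protocol 4.2 uses for eligibility; neither document sets it as an outlier threshold.
- Extension of the Day 1 minimum-heart-rate and time-to-minimum tables to Week 24 for switchers. These leave out at most 24 of 96 possible first etrasimod doses (24/96 = 25%).

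The cost is a few more descriptive tables from data already collected, and a short addition to the SAP. No visit, procedure or planned test changes.
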